Before any studies investigating the radioprotective effects of locally administered melatonin can be undertaken in humans, it is imperative that the pharmacokinetic properties of melatonin are investigated when administered in this way. No previous studies investigating the pharmacokinetics of vaginal, intravesical, or rectal administration of melatonin have been performed [23]. The few studies investigating transdermal administration of melatonin have been insufficient [24-26]; only one study has been able to estimate a $T_{1/2}$, and only in two volunteers [27], and no studies have investigated transdermal bioavailability [23].

Study design

Objective

The aim of the study is to determine the pharmacokinetic properties of, and possible adverse reactions of, melatonin when administered intravenously, rectally, intravesically, vaginally, and transdermally, in healthy female volunteers.

Design

This study is a crossover study, including five individual study sessions investigating five different routes of administration of melatonin. Four of the study sessions (intravenous, rectal, intravesical, and vaginal) will consist of one study day and one plasma sample the following day. The transdermal application will consist of one study day, followed by plasma samples at 24 and 48 hours following application. Between each study session, the subjects will have a washout period of a minimum of 7 days. The study will include a total of ten healthy female volunteers.

The subjects will participate in study sessions in the following order: intravenous, rectal, intravesical, vaginal, and transdermal administration. The study will be concluded after the

48-hour plasma sample after transdermal administration. Should a participant be menstruating at the time of the vaginal administration study session, the session will be postponed for one week.

Study course

Study session 1: Intravenous administration

The melatonin will be administered intravenously, followed by plasma samples over the following 24 hours. The intravenous melatonin will be dissolved in an ethanol/saline solution (2 ml 99.9 % ethanol/23 ml 0.9 % saline) containing 25 mg of melatonin. The infusion of melatonin will be performed over 10 minutes, the infusion rate being 2.5 mL per minute.

Study session 2: Rectal administration

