The melatonin will be administered rectally in a fluid, followed by plasma samples over the following 24 hours. The melatonin formulation applied for rectal administration will be a 2.5 ml fluid containing 25 mg of melatonin. The delivery of the fluid is to be performed via an enema. The subjects will be asked to defecate, if possible in the morning, prior to the administration of melatonin.

Study session 3: Intravesical administration

The melatonin/dimethyl sulfoxide (DMSO) aqueous solution will be administered intravesically, followed by plasma samples over the following 24 hours. The melatonin used in the study will be applied intravesically through a catheter at a dose of 25 mg in 50 ml of a solution of 50% (w/w) DMSO in water, the solution containing melatonin at a concentration of 0.5 mg/ml. The subjects will be asked not to consume fluids three hours prior to the start of the study day, and will be asked to void their bladder prior to administration of melatonin.

Study session 4: Vaginal administration

The vaginal suppository containing melatonin will be administered vaginally, followed by plasma samples over the following 24 hours. The melatonin used in the study will be applied at a dose of 25 mg in a suppository (Witepsol S58) vaginally, by the participant themselves.

Study session 5: Transdermal administration

The melatonin will be administered topically as 1 g of a 2.5% (w/w) melatonin cream over a skin area of 20 x 20 cm (400 cm²), followed by plasma samples over the following 48 hours. The dose of melatonin used in the study will thus be 25 mg. The participants will be asked to refrain from using any other creams or lotions one day prior to the study session, and for the following 48 hours.

Outcomes

The outcomes are identical for four of study sessions of the trial (intravenous, rectal, intravesical, and vaginal). The transdermal study session will have a follow-up of 48 hours rather than 24 hours. These differences are outlined below.

Primary outcome

Plasma concentration of melatonin at baseline, 0 min, 10 min, 20 min, 30 min, 40 min, 50 min, 1 hour, 2 hours, 3 hours, 4 hours, 6 hours, 8 hours, and 24 hours. Blood samples are drawn from a peripheral venous catheter within the first 8 hours, and the 24-hour samples will be taken as a single venipuncture. Each blood sample will have a volume of 6 ml, totaling 84 ml for each of the four first study sessions. For the blood samples drawn from a peripheral venous catheter, 4 ml of blood

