
will be drawn as “waste”, to ensure that the following 6 ml consist of undiluted blood, totaling another 52 ml of blood. In total, the subjects will have 136 ml of blood samples each study session.

For the transdermal study session, blood samples are drawn at baseline, 0 min, 30 min, 1 hour, 2 hours, 4 hours, 6 hours, 8 hours, 10 hours, 12 hours, 16 hours, 24 hours and 48 hours. Intervals are based on data from previous pharmacokinetic studies of transdermal melatonin [23]. Blood samples are drawn from a peripheral venous catheter within the first 16 hours, and the 24- and 48-hour samples will be sampled through a single venipuncture each. Each plasma sample will have a total volume of 6 ml, totaling 78 ml for the transdermal study session. For the blood samples drawn from a peripheral venous catheter, 4 ml of blood will be drawn as “waste”, to ensure that the following 6 ml consist of undiluted blood, totaling another 44 mL of blood. In total, the subjects will have 122 ml of blood drawn samples for the transdermal study session.

Plasma samples will be kept in a locked freezer (with a temperature-alarm) at the Department of Surgery, Herlev Hospital. The plasma concentration will be assessed by radioimmunoassay (RIA)-technique at Gastrolab, Herlev Hospital. RIA-technique is a validated method of determining melatonin in plasma that has been used for years [28]. A bio-bank will be created, containing solely the plasma samples from this study (see Data Management for further details). In the case report forms (CRF), the collection time of each sample will be noted. The plasma concentrations will be delivered to the investigator digitally from the laboratory, and will afterwards be noted in the through double entry CRF, by independently two investigators.

Secondary outcomes

Sedative effects and other adverse effects

A Karolinska sleepiness scale (KSS)-score will be performed at baseline and once every hour for 8 hours, as well as at 24 hours, and noted in the CRF. For the transdermal study session, the score will

be performed at every hour on the first day until 16 hours, as well as at 24 and 48 hours. The KSS is frequently used to evaluate subjective sleepiness. The scale has been validated against performance and EEG-variables [29].

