The volunteers can withdraw their consent at any point during the trial. The dropout criteria of the study are if a subject at some point during the study starts to fulfill any of the exclusion criteria, or if a subject is unable to participate in all five study sessions. Furthermore, the investigator can at any point exclude participants from the trial, if the investigator deems it necessary for the safety of the participant. The reason for a subject withdrawing their consent will be reported in the CRF. Data from dropouts will not be used in the statistical analysis.

Conclusion of the study

Each volunteer will have concluded the study after finishing all five study sessions. A total of ten subjects will be included in the study. In case of dropouts, the study will be concluded after a total of eight subjects have completed the study. If more than two subjects drop out, we will include further subjects until a minimum of eight subjects have completed the study.

Handling of melatonin formulations

Storage

Melatonin alcohol/saline solution

Dry melatonin will be packaged according to EU GCP/GMP-guidelines in containers with 25 mg melatonin. All containers with dry melatonin will be given a batch number. The 99.9% ethanol solvent will be packaged in ampoules and also be given a batch number. The melatonin, the 0.9% saline, and the 99.9% ethanol solvent will be acquired via Skanderborg Apotek.

Melatonin rectal fluid

The melatonin fluid, consisting 25 mg of melatonin dissolved in 2.5 mL of a 20% w/w glycofurol, and 40% w/w DMSO solution in water. This fluid has been demonstrated by Bioneer A/S to have no degradation of melatonin while being stored at 25°C for 45 days. Therefore, the fluid will be stored at room temperature. This fluid will be produced and packaged by Glostrup Apotek, according to GMP-guidelines. The fluid will be packaged in single dose mini enemas, and each box will contain 12 mini enemas.

Melatonin/DMSO solution

The melatonin will be dissolved into a 50/50% w/w DMSO and water solution at a concentration of 0.5 mg/g. This solution has been demonstrated by Bioneer A/S to have no degradation of melatonin while being stored at 25°C for 45 days. Therefore, the fluid will be stored at room temperature. The fluid will be packaged in single dose vials (50 ml), and each box will contain 12 vials. The melatonin/DMSO solution will be produced and packaged by Skanderborg Apotek, according to GMP-guidelines.

Melatonin suppository

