The suppository will consist of a Witepsol S58 base, containing 25 mg of melatonin. The Witepsol S58 base contains hard fat, polyoxyethylene (25) cetyl stearyl ether and glyceryl ricinoleate [30]. The suppositories will be stored at room temperature. The melatonin will be packaged as single dose suppository in blister packs. The sizes of the blister packs are to be decided. An applicator will possibly be included. The suppositories will be produced and packaged by Glostrup Apotek, according to GMP-guidelines.

Melatonin cream

The cream for transdermal application will consist of 25 mg/g melatonin as well as 150 mg/g DMSO, in a cream base. The dose for each application will be 1 g, and the cream will be packaged in 30 g tubes. The tubes will be stored at room temperature. The cream will be produced and packaged by Glostrup Apotek, according to GMP-guidelines.

Administration

A dose of 25 mg melatonin for local administration has been chosen. This dosage was based on the smallest doses that have demonstrated radioprotective effects in animals [7, 31-33]. The dose has been scaled for humans, taking into account that the effect aimed to achieve should be local, rather than systemic. All administrations of melatonin to the healthy volunteers will be performed by an investigator, except for the vaginal suppository and transdermal cream which will be administered by the subjects themselves.

Study session 1: Intravenous administration

On the day of the study, the intravenous solution will be prepared by an investigator: Two ml of ethanol (99.9%) will be aspirated into a 50 ml syringe. Two ml ethanol will be mixed into a glass of 25 mg dry melatonin, and aspirated back into the 50 ml syringe. Another 23 ml of saline 0.9% will be aspirated into the syringe. The solution will contain 25 mg melatonin in a 4 ml ethanol/46 ml saline solution (1 mg/ml). This solution will then be administered as a bolus through a venous line at an infusion rate of 2.5 ml/minute over 10 minutes. This method for delivering intravenous melatonin has been used in a previous pharmacokinetic study investigating exogenous melatonin administration [5, 34].

Study session 2: Rectal administration

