The number of patients needed for this study is not based on a power calculation. We have decided that 8 subjects are needed to collect information of how the plasma concentrations develop over time. Because of the risk of dropouts, we have chosen to include a total of 10 subjects.

Data will be presented as either mean (SD) or median (IQR), unless stated otherwise.

Data will be analyzed using IBM SPSS Statistics for Windows version 22.0 (IBM Corp., Armonk, NY, USA) and Graph Pad Prism version 7.0 (Graph Pad Software Inc., La Jolla, CA, USA).

Time to maximal concentrations (t_{\max}) and maximal plasma concentrations (C_{\max}) will be assessed directly at the relevant time points. The pharmacokinetic variables: absorption constant (k_a), absorption half-life ($t_{1/2}$ absorption), elimination rate constant (k_e) and elimination half-life ($t_{1/2}$ elimination) will be estimated by “the method of residuals” [57]. Areas-under-the-curve (AUC) of plasma concentrations will be calculated by applying the trapezoidal rule [58]. $AUC_{0-\infty}$ will be estimated as $AUC_{0-8 \text{ hours}} + (C_{8 \text{ hours}}/k_e)$. Bioavailability (f) will be calculated as follows:

$$f = 100 \times \frac{AUC_{0-\infty} (\text{rectal, intravesical, vaginal or transdermal}) \times D_{iv}}{AUC_{0-\infty} (iv) \times D_{\text{rectal, intravesical, vaginal or transdermal}}}$$
 where D represents the dose

administered.

Data monitoring and management

This study will be conducted in compliance with the protocol, the ICH-GCP guidelines and the applicable regulatory requirements. The standard procedures for quality control and quality assurance are followed in compliance with the ICH-GCP guidelines, and investigator/sponsor allows direct access to data/documents for monitoring, auditing, and inspection from both the Danish Medicines Agency (Lægemiddelstyrelsen) and the Good Clinical Practice (GCP)-unit. The GCP-unit will monitor the study. Data will be stored electronically on a secure server until 10 years

after the end of the study, after which all person-sensitive data are deleted. Blood samples will be destroyed after analysis, at a maximum of one year after sampling. A biobank will be created, solely containing these blood samples. Until analysis, the blood samples are kept in a locked freezer at -80°C (with a temperature-alarm) in a locked room at Gastroenheden D, Herlev Hospital. The blood samples will be analyzed with the RIA-technique at Gaslab, Herlev Hospital.

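### The half-life analysis does not use each subject's IV session to tell absorption from elimination; if the cream is absorbed slowly, its absorption half-life could be reported as elimination

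*Combined protocol and SAP*

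**What the plan says.** In Statistics, ka, absorption half-life, ke and elimination half-life are all assigned to one technique, without distinguishing routes: "elimination half-life ($t_{1/2}$ elimination) will be estimated by “the method of residuals” [57". No rule says which of the two fitted slopes is absorption. The IV data appear only as the AUC and dose reference in the bioavailability formula. The symbol ke is used again for the extrapolated area: AUC to infinity "will be estimated as $AUC_{0-8 \text{ hours}} + (C_{8 \text{ hours}}/k_e". The session that supplies this ke is not stated.

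Three other places bear on the point.

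- **An IV reference exists for everyone analysed.** Under Design: "The subjects will participate in study sessions in the following order: intravenous, rectal, intravesical, vaginal, and transdermal administration". Under Withdrawal and dropout criteria, a subject who cannot attend all five sessions is a dropout, and "Data from dropouts will not be used in the statistical analysis".
- **The cream is followed for longer.** Under Outcomes: "The transdermal study session will have a follow-up of 48 hours rather than 24 hours". Under Primary outcome: "Intervals are based on data from previous pharmacokinetic studies of transdermal melatonin [23".
- **A transdermal half-life is a named gap.** The background before Study design says of transdermal melatonin that "only one study has been able to estimate a $T_{1/2}$, and only in two volunteers".

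**The concern.** The method of residuals fits a line to the late log-concentrations, subtracts it, and fits a second line to the early residuals. It returns a slow rate and a fast rate. Calling the slow one elimination is a convention that holds only when the drug enters the blood faster than it leaves. When entry is slower, the late slope describes release and absorption from the formulation.

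The half-lives are named results of a study whose aim is pharmacokinetic description, and the protocol presents the scarcity of transdermal half-life data as a reason for doing it. A cream absorption half-life published as an elimination half-life would fill that gap with the wrong quantity.

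The documents make slow absorption plausible for the cream through its longer sampling. For the vaginal suppository it is only possible; the one hint is its base ("The Witepsol S58 base contains hard fat"). The same silence covers the rectal and intravesical routes.

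**Working it through.** The plan states no half-life, ka or ke, so there is no figure to reproduce. The rates below are assumptions. The sampling times are the protocol's.

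**Model.** One compartment with first-order absorption, in units where F × D / V = 1:

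C(t) = ka / (ka − ke) × [exp(−ke t) − exp(−ka t)], with each rate = ln 2 / half-life.

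**Step 1: one curve cannot show the order.** Exchanging ka and ke leaves the bracketed shape the same and changes the multiplier from ka to ke. The two curves therefore differ by the constant ratio of the rates. For half-lives of 4 h and 0.75 h this is 4 / 0.75 = 5.33 at every sampling time. In a non-IV curve taken alone, that constant is absorbed into the unknown F / V.

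**Step 2: apply the method to the cream** (elimination 0.75 h, absorption 4 h). The multiplier is 0.75 / (4 − 0.75) = 0.2308.

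- Late samples at 16, 24 and 48 h: 0.01442, 0.003606 and 0.0000563. From 16 to 48 h the fall is 256-fold, so the slope is ln 256 / 32 = 0.1733 per h and the half-life is 4.0 h. This would be labelled elimination.
- Residuals at 0.5, 1 and 2 h: 0.1454, 0.0916 and 0.0363. From 0.5 to 2 h the fall is 4-fold, so the slope is ln 4 / 1.5 = 0.924 per h and the half-life is 0.75 h. This would be labelled absorption.

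The 48 h sample is not essential: a late fit on 10 to 24 h also gives 4.0 h and 0.75 h.

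**Step 3: vary the assumed absorption half-life** (elimination 0.75 h, no noise).

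| Assumed absorption, h | Schedule | Labelled elimination, h | Labelled absorption, h |
|---|---|---|---|
| 0.25 | cream | 0.75 | 0.25 (correct) |
| 2 | cream | 2.0 | 0.75 |
| 4 | cream | 4.0 | 0.75 |
| 4 | vaginal, late fit 6/8/24 h | 4.0 | 0.74 |
| 8 | cream | 8.0 | 0.75 |
| 12 | cream | 12.0 | 0.75 |

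**Step 4: the AUC tail.** If the labels are corrected and the IV ke is then carried into C8/ke, the area comes out too small. By mass balance, AUC(0–8) + C8/ke equals the amount absorbed by 8 h divided by clearance. Its ratio to the true AUC is therefore 1 − 2^(−8 / absorption half-life):

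- 2 h: 1 − 2^(−4) = 94%
- 4 h: 1 − 2^(−2) = 75%
- 8 h: 1 − 2^(−1) = 50%
- 12 h: 1 − 2^(−0.667) = 37%

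With the route's own late slope the ratio is 99.9% in all four cases. At 4 h, AUC(0–8) is 69.2% of the true area. The tail adds 5.8% with IV ke, and 5.8% × 4 / 0.75 = 30.7% with the route's own slope.

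**The case against.** The strongest reply is that silence is not a plan to mislabel. An analyst could compare each late slope with the subject's IV session and still comply with Statistics, and the cited method source, which cannot be consulted here, may address the matter. That is fair. The text does not require the comparison, however, so the label could be settled after the results are seen.

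A reader might infer more than the documents support in three ways.

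- *That the cream half-lives will be swapped.* No absorption or elimination rate is given. Longer sampling is compatible with slow absorption but does not demonstrate it. If absorption is fast, the usual labels are right.
- *That bioavailability or the primary outcome is biased.* Concentrations, Cmax and tmax do not depend on the labels. On the natural reading, each session's ke comes from its own curve, and then AUC and f are also sound. The losses in Step 4 would come from a half-finished correction; they are not a demonstrated fault of the plan.
- *That a fixed numerical cut-off for labelling is needed.* A strict margin would withhold many correct ka values if absorption is fast. Its performance would also be uncertain if endogenous melatonin is left uncorrected in the late samples.

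The background passage, moreover, speaks of a transdermal half-life, not specifically an elimination one. A clearly named terminal half-life would answer it.

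**Conclusion.** The gap is real, conditional and minor. Statistics does not use the IV session to identify elimination. Where absorption is the slower process, the usual convention reports the absorption half-life as elimination: 4.0 h in place of 0.75 h in the worked case, and 2 to 12 h across the assumed range. The harm is confined to ka, ke and their half-lives, provided the tail uses each route's own slope.

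The size rests on assumed rates, a one-compartment model and noise-free data without endogenous background. That exchanging the rates only rescales the curve does not depend on the rates chosen.

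**What to change.** Add to Statistics:

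1. Estimate ke and elimination half-life from each subject's IV session, and report no ka for that session, since an infusion has no absorption phase.
2. For the rectal, intravesical, vaginal and transdermal routes, report the late slope as an apparent terminal rate and half-life beside the subject's own IV value. Call a slope absorption or elimination only where the comparison with IV clearly supports it.
3. State that C8/ke uses each route's own terminal slope, not the IV ke.

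This takes a few sentences and a short calculation, with no new samples. There are two costs. It assumes that elimination is stable between sessions; with four washouts of at least 7 days, IV and cream are at least 4 × 7 = 28 days apart. Some profiles will also yield no ka.

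### The Statistics section does not say which samples define the elimination slope and makes no use of the pre-dose melatonin baseline, so half-life depends on an unstated choice

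*Combined protocol and SAP*

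**What the plan says.** The Statistics section is the only analysis text. The absorption and elimination constants and both half-lives "will be estimated by “the method of residuals” [57". It continues: "Areas-under-the-curve (AUC) of plasma concentrations will be calculated by applying the trapezoidal rule [58". AUC to infinity is the area to 8 h plus C8/ke, and bioavailability f is the dose-adjusted ratio of that quantity to its intravenous counterpart. No terminal window, minimum number of points or fit criterion is given. No formula contains the baseline.

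Under Primary outcome, sessions 1–4 begin with "Plasma concentration of melatonin at baseline, 0 min, 10 min, 20 min" and end with "4 hours, 6 hours, 8 hours, and 24 hours", so the only sample after 8 h is at 24 h. For the cream, "For the transdermal study session, blood samples are drawn at baseline, 0 min, 30 min, 1 hour, 2 hours, 4 hours", and sampling runs on to 48 h. The Setting section confirms that the baseline is drawn before administration. The opening background describes melatonin as a hormone made by the pineal gland.

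**The concern.** Late samples hold drug plus whatever the body makes. Once the drug has gone, the log concentration levels off at the background. A late sample included in a log-linear fit then flattens the slope and lengthens the half-life. The risk is greatest in sessions 1–4: if the true half-life is 0.75 h, the 24 h sample comes 24/0.75 = 32 half-lives after dosing and is essentially background. It also sits 16 h beyond its nearest neighbour, so it has high leverage.

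Two analysts following the text could therefore report clearly different half-lives from the same tubes. Half-life is one of the pharmacokinetic properties the study sets out to determine. Because ke also enters the C8/ke term, some of the effect passes into f.

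**Working it through.** The plan states no half-life, clearance or background level, so there is no figure of its own to reproduce. The check models profiles at the plan's sampling times.

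**Inputs from the documents.** Dose 25 mg = 25×10⁹ pg. For the intravenous session, "The infusion of melatonin will be performed over 10 minutes", so T = 1/6 h. Sampling times and the AUC and f formulas are as written.

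**Assumptions, not in the documents.** Clearance CL 40–90 L/h; true half-life 0.75 h (0.5, 1.0 and 1.5 h also tried); one compartment; absorption constant 3 per h for fast routes; absorption half-life 4–8 h for slow transdermal uptake; constant background B of 5–10 pg/ml.

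**One intravenous case by hand** (CL 90, B 10, time from start of infusion):
- k = ln 2/0.75 = 0.924 per h.
- After the infusion, C(t) = (Dose/T)/CL × (1 − e^(−kT)) × e^(−k(t−T)). This gives 6884, 1084, 170.7 and about 0.00006 pg/ml at 4, 6, 8 and 24 h.
- Adding B gives 6894, 1094, 180.7 and 10.0, with logs 8.838, 6.998, 5.197 and 2.303.
- Slope on 4, 6, 8 h: (5.197 − 8.838)/4 = −0.910, so half-life = 0.693/0.910 = 0.76 h.
- Slope on 4, 6, 8, 24 h: mean time 10.5 h, Sxx = 251, Sxy = −70.84, slope −0.282, so half-life = 0.693/0.282 = 2.46 h.

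**Half-life over the full assumed ranges, true value 0.75 h:**

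| Route | 4, 6, 8 h | 4, 6, 8, 24 h |
|---|---|---|
| Intravenous | 0.75–0.76 h | 1.9–2.5 h |
| Fast, F = 10% | 0.77–0.83 h | 2.7–3.9 h |
| Fast, F = 1% | 0.91–1.31 h | 4.9–8.9 h |

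Starting the clock at the end of infusion, or treating the dose as a bolus, changes the 1.91–2.46 h intravenous result only to 1.96–2.53 h or 1.93–2.49 h.

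**Sensitivity to the true half-life** (intravenous, 24 h included): 2.7–3.8 h if the truth is 0.5 h; 1.7–2.1 h if 1.0 h; 1.64–1.89 h if 1.5 h, where 1.64/1.5 = 1.1 and 1.89/1.5 = 1.3.

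**Effect on f.** For F between 0.1% and 10% the absolute rise is 0.007–0.05 percentage points for fast routes on 4–8 h, and 0.015–0.21 points with 24 h included. Slow absorption gives 0.014–0.14 points. In relative terms, slow transdermal uptake at F = 1% raises f by about 1–11% on 4–8 h. At the upper end, f goes from 1.019% to 1.132%, and 1.132/1.019 = 1.11. With absorption half-life 8 h, C8/ke is about 57–60% of the AUC to infinity, which is why ke matters there. Adding 24 h raises the shift to as much as 16% (0.967% to 1.118%), and using 48 h raises it further.

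**Transdermal half-life at F = 1%.** The apparent value rises 1–7% on 4–8 h and 3–28% with 24 h added. Under this assumption the terminal slope reflects absorption rather than elimination.

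**Night-time rise.** This assumes 5 pg/ml by day, a peak of 30–60 pg/ml at 18 h, F = 1% and a true apparent half-life of 8.0 h. The slope gives 9.9–28 h on 8–16 h but 5.6–7.3 h on 16 and 24 h, so the error can go either way. Subtracting the daytime value leaves 9.7–27 h and 5.2–7.0 h.

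**The case against.** The strongest reply is that the plan never says the 24 h sample enters the slope. Its AUC stops at 8 h and its tail is C8/ke, so ke is most naturally the decay rate around 8 h. On that window the bias nearly vanishes for intravenous and well-absorbed routes. A line through 24 h would also fit visibly badly: in the modelled intravenous case R² is 0.86–0.93, against 1.000 on 4–8 h. This largely stands. The 8 h limit is written only for AUC, however, the 24 h value belongs to the primary outcome, and no fit criterion is set.

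Reference 57, cited for the method, may define a window. That cannot be seen from the documents, so the provable statement is that the plan's own text does not.

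A reader might infer that the reported half-lives will be several-fold too long. The documents do not support that: it needs both the 24 h sample in the slope and a true half-life of about 0.75 h or less. A reader might also tie the several-fold error to the transdermal gap noted in the rationale, where half-life was estimated in one study "and only in two volunteers [27], and no studies have investigated transdermal bioavailability". The large errors modelled here belong to intravenous and fast-absorbed routes; the flat-background transdermal error is far smaller. Nor does the point overturn the bioavailability results, since a poorly absorbed route would still be read as poorly absorbed. Equally, it is too broad to call the effect on f small without saying that this means percentage points.

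**Conclusion.** The point holds as a gap in specification with a better method readily available. The plan derives ke, half-life, AUC, C8/ke and f from total concentrations of an endogenous hormone, leaves its own baseline samples unused, and does not name the samples that define ke. That much needs no assumption.

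The size does rest on assumptions. On 4–8 h the matter is minor except near 1% bioavailability. With 24 h in the slope, intravenous half-life is about 2.5 to 3.3 times too long at a true 0.75 h (1.9/0.75 and 2.5/0.75), about twofold at 1.0 h and 1.1–1.3 times at 1.5 h. The study is descriptive, with no hypothesis test, so no formal conclusion turns on this. It is a worthwhile, low-priority change; confidence is medium because none of the governing quantities is in the documents.

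**What to change.** In the Statistics section:

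1. Define ke, for each route, by prespecified terminal-phase samples or a selection rule fixed in advance. Leave out samples at baseline level (24 h in sessions 1–4; 24 h and 48 h for the cream when at baseline) and use them as a check of return to baseline.
2. Report AUC, ke, half-life and f after subtracting each session's own pre-dose value, beside the uncorrected values. Set the tail term to zero when corrected C8 is not above 0.
3. State as a limitation that one pre-dose value does not remove a night-time rise in late transdermal samples.

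The first change alone nearly suffices for intravenous and well-absorbed routes. The second matters mainly at low bioavailability. For Cmax it is negligible: 5–10 pg/ml against a modelled intravenous peak of about 240,000–530,000 pg/ml. Subtraction without the first change is not enough. With an assumed per-sample SD of 1.5 pg/ml, the corrected 24 h value is positive in half of profiles, and the intravenous half-life in those still has a median of 1.6–1.8 h.

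All samples are already planned, so the cost is wording plus some noise at very low concentrations. With the same SD, F = 1% and a 4–8 h slope after subtraction, the median half-life is 0.75–0.78 h. One subject's 95% range is 0.54–0.89 h at clearance 40 L/h and 0.45–1.04 h at 90 L/h. Corrected C8 is not above 0 in 1–14% of profiles. At F = 10% the range stays within 0.71–0.79 h.
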